11.4 Reporting a Death

If a site becomes aware of a subject's death, phone or electronic notification to the Sponsor or Sponsor's designee is expected within 24 hours of site learning of the death. Completed appropriate CRF(s) should be submitted to the sponsor within 48 hours of learning of the event.

In addition, the following materials must be submitted to the Sponsor or Sponsor's designee as soon as possible:

- A copy of the subject's death certificate.
- Any additional requested information if available (e.g., hospital records and autopsy reports).

11.5 Protocol Deviations

Each Investigator should conduct the study in compliance with the Study Protocol. Any deviation from the Study Protocol will be documented on appropriate CRFs by explaining the deviation and corrective actions taken to prevent possible re-occurring deviations. Any emergency deviations (deviations from the study protocol to protect the life or physical wellbeing of a subject) must also be reported to the Sponsor within 48 hours and the site EC per their local guidelines.

11.6 Device Malfunctions

A device malfunction is defined as any inadequate performance of the study device when used per the most current IFU. Each device malfunction will be reported on the appropriate CRF by the site. Every effort must be made by the site to return the suspected device to the Sponsor for analysis. All device performance issues/malfunctions will be reported in the clinical results (e.g., final report). Device malfunction by itself should not be reported as AE unless it led to the new medical condition or worsening of pre-existing condition or met the definition of an Adverse Device Effect in Section 11.1.5.

12 CLINICAL EVENTS COMMITTEE (CEC)

The purpose of the CEC is to complete unbiased reviews and classification of adverse events. The CEC will consist of physicians who are not Investigators in the Veniti Trial and who do not have any significant investment in Sponsor's or any of their entities. Committee membership will be limited to the specialties of interventional cardiology, vascular surgery, or interventional radiology.

13 DATA SAFETY MONITORING BOARD (DSMB)

The purpose of the DSMB committee is to complete unbiased review of all safety data in comparison to the established criteria in order to determine if the rate of SAEs is acceptable, to evaluate interim data analysis results, to provide related advice on study STE-HUM-007P US Clinical Protocol Revision C

Confidential

Page 37 of 70

management and progress, and to make any recommendations regarding the study protocol. Members of the DSMB will be comprised of a multidisciplinary group of physicians and a biostatistician, they will not be employees or shareholders of Veniti, Inc., and they will not be participating VIRTUS Investigators.

The DSMB will be responsible to communicate any safety, scientific concerns, or other perceived concerns to Veniti or Veniti's designee as soon as possible. The DSMB will provide, after each scheduled meeting, written recommendation regarding the continuation of the trial, early stopping, or any suggested changes for the conduct of the trial. Veniti is responsible for informing the IEC if the DSMB has advised them of any major safety concerns and has recommended the study be stopped or if they have made any recommendations to alter the study.

DSMB decisions are final and non-negotiable by the sites.

14 INVESTIGATIONAL DEVICE DISTRIBUTION AND TRACKING

Investigators are prohibited from providing an investigational device to any person not authorized to receive it (21 CFR 812.110(c)). Investigators must also maintain complete, current, and accurate records of the receipt, use, or disposition of investigational devices (21 CFR 812.140(a)(2)) that relate to:

- The type and quantity of the devices received at the site, dates of receipt, and lot numbers (or other reference numbers) for each received device,
- The type and quantity of the devices received returned to the Sponsor or disposed at the site,
- Name of person who received or dispose each device,
- Subject number(s) correlated to each used device.

Upon completion or termination of the study (or the Investigator's part of the study), or at the Sponsor's request, an Investigator is required to return to the Sponsor any remaining supply of the device or otherwise to dispose of the device as the Sponsor directs (21 CFR 812.110(e)).

15 STATISTICAL METHODS

15.1 Overview of Study Design

This study will be a single-arm trial compared to performance goals developed from the medical literature (See Section 15.5). Enrollment will be stratified according to etiology of disease. A total of 125 subjects (approximately 74% of enrollees) enrolled in the pivotal arm will have obstruction associated with thromboembolic disease (post-thrombotic, PT). A total of 45 subjects (approximately 26% of enrollees) enrolled in the pivotal arm will have pivotal arm will have iliofemoral venous segment obstruction without previous thrombo-embolic disease without intraluminal disease (non-thrombotic, NT). The feasibility stage will aim to acrue approximately the same relative proportion of NT:PT subjects.

STE-HUM-007P US Clinical Protocol Revision C

15.2 Missing Data

Every effort will be made to collect all data points in the study. The sponsor plans to minimize the amount of missing data by appropriate management of the prospective clinical trial, proper screening of study subjects, and training of participating investigators, monitors and study coordinators. The sponsor will provide a list of patients who do not complete the trial along with the best information available on why the each left the trial prematurely.

15.3 Primary Analysis: Per-protocol

All patient data that is available on subjects who drop out during the course of the study will be included. In the primary analysis of the primary endpoints, we will assume that data are missing at random (i.e., it is not the study treatment that is causing the data to be missing) and ignore missing values in the analyses.

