9.10 Interval Evaluation

At any point following the venous stenting procedure, the patient may present with symptoms of clinically significant obstruction of the target vessel. Patients with possible obstruction should undergo all medical examinations and interventions as deemed appropriate for medical care. All technical examinations (DUS, IVUS, or venograms) obtained during the course of the evaluation will be submitted as part of the case report form and will be submitted to the Core Laboratory for determination of primary endpoint.

Patients who undergo re-intervention, but who are found on Core Laboratory assessment to have vessel patency prior to the re-intervention will not be counted as a primary efficacy endpoint failure. Patients who undergo an interval evaluation but do not receive an intervention will have their status (patency/non-patency) determined by the Core Laboratory. Patients who are found to be patent by Core Laboratory analysis will continue in the study through 12 months.

Patients who undergo another intervention at any time prior to the 12 month evaluation, or who are found to have in-stent stenosis > 50%, by Core Laboratory assessment, will be considered to have failed the primary efficacy endpoint and will not be required to have further assessment of vessel patency or other secondary endpoints.

All patients will complete the 30-day safety assessment regardless of primary patency status.

9.11 24 Month Evaluation (730 days ± 90 days)

- Telephone follow-up for SAE assessment. May be performed in-person, at the discretion of the investigator.
- Duplex ultrasound to assess vessel patency. (Office or laboratory visit)

9.12 36 Month Evaluation (1,095 days ± 90 days)

- Telephone follow-up for SAE assessment. May be performed in-person, at the discretion of the investigator.
- Duplex ultrasound to assess vessel patency. (Office or laboratory visit)

STE-HUM-007P US Clinical Protocol Revision C

Confidential

Page 31 of 70

9.13 48 Month Evaluation (1,460 days ± 90 days)

• Telephone follow-up for SAE assessment. May be performed in-person, at the discretion of the investigator.

9.14 60 Month Evaluation (1,825 days ± 90 days)

• Telephone follow-up for SAE assessment. May be performed in-person, at the discretion of the investigator.

STE-HUM-007P US Clinical Protocol Revision C

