11.1.4 Major Adverse Event (MAE)

All **major adverse events (MAEs)** must be reported within 24 hours of knowledge of the event to the Sponsor or Sponsor Designee. A subcategory of SAEs include any of the following primary safety endpoints occurring within 30 days of the study procedure:

- Device or procedure-related death
- Device or procedure-related bleeding at the target vessel and/or the target lesion or at the access site requiring surgical or endovascular intervention or blood transfusion ≥2 units
- Device or procedure-related arterial or venous injury occurring in the target vessel segment and/or target lesion location or at the access site requiring surgical or endovascular intervention
- Device or procedure related acute DVT outside of the target vein segment
- Clinically significant pulmonary embolism defined as being symptomatic with chest pain, hemoptysis, dyspnea, hypoxia etc... AND be documented on CT
- Embolization of stent

These events may also need to be reported per requirements of the reviewing EC.

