15.8 Evaluation of Endpoints

15.8.1 Primary Efficacy Endpoint

The primary efficacy endpoint for this study will be the primary patency rate at 12 months post-intervention. Stented limbs will be assigned the status of *patency failure* if they are known to have a patency failure event:

- Thrombosis including the stented area of the vein
- Re-intervention including the stented area
- Venous imaging study at any time through 12 months showing a restenosis of greater than 50%.

Patients will be assigned the status of *patency success* if their venous imaging study at 12 months showed no greater than 50% restenosis (and no prior study showed greater than 50% restenosis).

STE-HUM-007P US Clinical Protocol Revision C

In the per-protocol (PP) analysis, only patients that meet either of these two criteria will be included. Patients with no imaging study at 12 months and no patency failure event will be ignored in the analysis.

In the worst-case and tipping point analyses, all patients will be included. Patients who were ignored in the PP analysis will be treated as patency failures.

Both the PP and worst-case analyses will test the following hypotheses:

$$\begin{aligned} \mathsf{H}_{0} &: q_{NT} * (p_{NT} - PG_{NT}) + q_{PT} * (p_{PT} - PG_{PT}) \le 0 \\ \mathsf{H}_{A} &: q_{NT} * (p_{NT} - PG_{NT}) + q_{PT} * (p_{PT} - PG_{PT}) > 0, \end{aligned}$$

where p_{NT} and p_{PT} are the observed 12-month patency rates for NT and PT subjects, respectively; PG_{NT} and PG_{PT} are pre-specified fixed performance goals for NT and PT subjects, respectively; and q_{NT} and q_{PT} , both are fixed weights for NT subjects (0.26) and PT subjects (0.74), respectively. The sample weights will not be adjusted based on actual enrollment rates.

The hypothesis test for this endpoint will be tested using a one-sided weighted Z-test at the 0.025 significance level. The test statistic for this hypothesis test is:

$$Z = \frac{q_{NT} * (p_{NT} - PG_{NT}) + q_{PT} * (p_{PT} - PG_{PT})}{\sqrt{q_{NT}^2 * \frac{PG_{NT}(1 - PG_{NT})}{n_{NT}} + q_{PT}^2 * \frac{PG_{PT}(1 - PG_{PT})}{n_{PT}}}$$

where p_{NT} is the proportion of successes in the NT population, PG_{NT} is the performance goal of 85.5% for the NT population, q_{NT} is the predefined weight of 0.266 for the NT population, p_{PT} is the proportion of successes in the PT population, PG_{PT} is the performance goal of 67.9% for the PT population, q_{PT} is the pre-defined weight of 0.74 for the PT population.

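### The primary patency analysis would drop a patient who dies from the device or procedure before 12-month imaging, against its own assumption that treatment does not cause missing data

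*Combined protocol and SAP*

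**What the plan says.** Section 15.3 (Primary Analysis: Per-protocol) states the premise, "we will assume that data are missing at random (i.e., it is not the study treatment that is causing the data to be missing", and the consequence for the primary endpoints, which is to "ignore missing values in the analyses".

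Section 15.8.1 turns this into a scoring rule. Three things make a patency failure:
- "Thrombosis including the stented area of the vein"
- "Re-intervention including the stented area"
- restenosis above 50% on imaging at any time through 12 months.

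Success requires a 12-month imaging study without such restenosis. For everyone else, "Patients with no imaging study at 12 months and no patency failure event will be ignored in the analysis".

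Section 11.1.4 lists "Device or procedure-related death" among the major adverse events, which count toward the primary safety endpoint if they occur within 30 days. No section classifies such a death for patency. Section 15.2 promises a list of non-completers "along with the best information available on why the each left the trial prematurely", but no scoring rule uses those reasons.

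Section 15.3.1 adds worst-case and tipping-point analyses and calls them supportive. Section 15.7 defines trial success by the weighted test plus the two observed stratum rates exceeding their goals. It gives the sensitivity analyses no role.

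**The concern.** The plan glosses its missing-data assumption in causal terms: treatment is not the reason the value is missing. A device- or procedure-related death without an earlier patency event is a clear counterexample, yet the rule treats it like a patient who moved away.

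The safety endpoint does not fully cover the gap. It stops at 30 days, so a related death on day 31 or later with no patency event counts against the device in neither primary endpoint.

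This is a single-arm test against fixed goals, so no control arm absorbs the effect. Compared with counting the death as a failure, dropping it can only raise the patency rate.

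**Working it through.** **Inputs.** From 15.7 and 15.8.1: goals 0.679 (PT) and 0.855 (NT); planned rates 0.779 and 0.955; weights 0.74 and 0.26; one-sided 0.025; 156 evaluable. (15.8.1 also prints 0.266 for the NT weight; 0.26 is used here, as in both hypothesis statements.) From 15.1: 125 PT and 45 NT enrolled. *Assumption:* the 156 split as 115 PT and 41 NT (156 × 0.26 = 40.6).

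**Reproducing the plan's power.**
- Null standard error = √(0.26² × 0.855 × 0.145/41 + 0.74² × 0.679 × 0.321/115) = 0.0352.
- Required margin over the goals = 1.96 × 0.0352 = 0.069, or 6.9 points.
- Standard error at the planned rates = √(0.26² × 0.955 × 0.045/41 + 0.74² × 0.779 × 0.221/115) = 0.0298.
- Power = Φ((0.100 − 0.0691)/0.0298) = Φ(1.04) = 85.0%. Exact enumeration of the two binomials gives 86.9%.

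The plan states 84% in one place and at least 85% in another, so the set-up matches to within 3 points.

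**Effect of one dropped death on the estimate, at the planned rates.**
- PT: 0.74 × 0.779 × (1 − 115/116) = 0.0050, or 0.50 points.
- NT: 0.26 × 0.955 × (1 − 41/42) = 0.0059, or 0.59 points.

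**Effect on false success.** Let true patency, counting related deaths as failures, equal the goals. If k deaths are dropped from a stratum and n patients are kept, the success probability among those kept is goal × (n + k)/n. For one PT death this is 0.679 × 116/115 = 0.685; for one NT death, 0.855 × 42/41 = 0.876. Enumerating both binomials with the Z statistic of 15.8.1 gives:

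| Related deaths dropped (assumed) | Z-test alone | With the two observed-rate conditions of 15.7 |
|---|---|---|
| None | 2.7% | 2.2% |
| One PT | 3.6% | 2.9% |
| One NT | 3.8% | 3.3% |
| Two PT | 4.6% | 3.7% |
| One PT, one NT | 4.9% | 4.3% |

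Two deaths both in the smaller NT stratum (0.855 × 43/41 = 0.897) give 5.1% for the Z-test.

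**A different denominator.** Starting from all 170 enrolled (125 PT, 45 NT) and spreading the losses evenly, the Z-test rate goes from 2.4% to 3.5% with one dropped and 4.3% with two. Direction and size agree.

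**Can the worst-case analysis stand in?** At the planned rates among evaluable patients, score all 170 − 156 = 14 non-evaluable patients as failures. The rates become 0.955 × 41/45 = 0.870 and 0.779 × 115/125 = 0.717. Then Z = (0.26 × 0.0151 + 0.74 × 0.0377)/0.0338 = 0.94, well below 1.96. A device performing exactly as planned would fail, so that analysis says little about the few losses the device itself caused.

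**The case against.** **Such deaths may never occur.** Section 4.2 reports no deaths in the published stenting literature, and 15.7.1 expects about 1% for the whole safety composite (about 1.7 of 170). This stands. A reader might infer that patency *is* overstated; the documents support only that it *would be* if such a death occurs.

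**The plan already handles missing outcomes.** Known failures are kept, reasons for leaving are listed, and the worst-case and tipping-point analyses treat every dropped patient as a potential failure. This is fair, and the plan does not hide these patients. But those analyses do not decide success, and they mix related with unrelated losses.

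**Patency is a vessel outcome, and the goals come from series whose definition has no death component.** If a related death scores as a failure in this trial but not in the source series, the comparison could shift. Section 4.2's statement that no deaths have been reported answers this: the same rule would have left the historical rates unchanged.

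**Embolization and device-related withdrawal.** A reader might want both scored as primary failures too. The documents do not support that. Embolization does not itself make the 12-month result missing, since the patient is still due for imaging. Section 9.10 may also already count a retrieval, because it fails "Patients who undergo another intervention at any time prior to the 12 month evaluation", subject to its core-laboratory exception. After a device-related withdrawal the stent may be open, and no section has the Clinical Events Committee (CEC) adjudicate withdrawal reasons.

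**Larger counts.** One could note that the exact safety test at n = 170 tolerates four events, and that four dropped patients would give 7.6-8.0%. That needs every tolerated event to prevent imaging. Most listed events (bleeding, vessel injury, DVT elsewhere, pulmonary embolism) do not inherently do so. Four is not a realistic anchor.

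**Conclusion.** The concern holds in a narrow, conditional form. The premise in 15.3 and the rule in 15.8.1 conflict for a device- or procedure-related death before 12-month imaging with no earlier patency event. Each such death, if dropped rather than failed, lifts weighted patency by about 0.5 (PT) or 0.6 (NT) points. The Z-test's false-success rate rises from 2.7% to 3.6-3.8% with one and to 4.6-4.9% with two, at least one of them PT.

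These figures assume a 115/41 evaluable split, true patency exactly at the goals, and a related death counted as non-patent. The number of such deaths is not in the documents; with none, nothing changes. The gap is worth closing because it is unambiguous, always favors the device and costs almost nothing to settle before data are seen.

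**What to change.** - **15.8.1:** add a fourth patency-failure criterion for the primary analysis: a death before 12-month imaging that the CEC adjudicates as device- or procedure-related. State that the CEC judges relatedness for every death up to that point, not only within 30 days.
- **15.3:** limit the missing-at-random assumption to losses not attributed to the device or procedure. Handling of all other missing patients in the primary analysis stays as it is.
- **15.3.1:** add a sensitivity analysis that also fails patients with no 12-month imaging after stent embolization, or after a withdrawal documented under 15.2 as due to a device-related adverse event. These should not become primary failures.

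The cost is about one sentence in each section and adjudication of any later deaths. Reported patency falls by about 0.5-0.6 points per related death, and not at all if there are none.

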15.3.1 Sensitivity Analyses: Worst-case and Tipping point

Supportive, sensitivity analyses will be performed to assess the impact of missing endpoint data. In the worst-case analysis, subjects with missing primary endpoints will be analyzed as failures with regard to that endpoint. For the primary efficacy endpoint, patients with missing data will be treated as clinical failures, i.e., re-stenosed or occluded stents. For the tipping-point analysis, the number of subjects with missing data required to be failures in order to reverse the trial conclusion will be determined.

15.4 Poolability Analysis

This study will be conducted such that 1) the same protocol will be used at each site; 2) site investigators and personnel will receive uniform training; and 3) central data management and monitoring will be applied with equal rigor at all sites. The diversity of settings will add to the scientific validity and generalizability of the findings.

Two types of poolability analyses will be performed to assess whether the data from the centers can be treated as one population: 1) on the patient demographic variables, and 2) on the endpoint data. Centers with fewer than 10 implants will be treated as a single center.

For the assessment of patient demographic variables, centers will be compared using a random-effects ANOVA for continuous variables such as age, or a random-effects logistic regression for categorical variables such as sex.

For the assessment of the primary endpoints, both of which are binary (Y/N or S/F) variables, a random-effects logistic regression will be used to assess the comparability of results across centers.

STE-HUM-007P US Clinical Protocol Revision C

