8 PATIENT POPULATION

A maximum of 200 patients at 45 centers worldwide will be enrolled. Thirty feasibility patients will be enrolled at approximately 7 - 10 centers and 170 pivotal patients will be enrolled at approximately 45 centers worldwide. A minimum of 114 pivotal patients will be enrolled at US centers.

The 12-month data from at least 156 evaluable pivotal patients, as well as detailed summary data on the 30 feasibility patients will be submitted to FDA to support a Pre-Market Approval (PMA) application.

Patients will include symptomatic adults ≥18 years of age with clinically significant chronic non-malignant obstruction of the iliofemoral venous outflow tract.

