15.7.1 Primary Safety Endpoint

None of the case series in the literature used pre-specified adverse event definitions. The complication rate appears to be low, but there are no controlled studies to indicate what a true adverse event rate might be under controlled reporting conditions. It is expected that the true rate of the pre-specified safety endpoint will be approximately 1%. The primary safety evaluation will test the following hypothesis:

 $H_{O}:\ P_{Vici} \leq 0.94$

$$H_A: P_{Vici} > 0.94,$$

where P_{Vici} is the freedom from event rate of pre-specified safety events associated with use of the Veniti Vici Venous Stent and 0.94 is the prespecified performance goal. The hypothesis will be tested under a onesided, one-sample exact binomial test. The hypothesis will be tested at the 2.5% significance level, and approximately 170 subjects provide greater than 90% power. Power was calculated using PASS 2008 software.

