15.9.1 Procedural Endpoints

Procedural technical success. The proportion of limbs with procedural technical success and the 95% CI will be reported.

Lesion success. The proportion of limbs with lesion success and the 95% CI will be reported.

Procedural success. The proportion of limbs with procedural success and the 95% CI will be reported.

Late technical success. The proportion of limbs with late technical success and the 95% CI will be reported.

Subgroup analysis. A subgroup analysis will be performed to evaluate device performance across genders.

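### The center poolability model for patency names no etiology term, so it mixes case mix with center effect; for safety the same model is uninformative at about 1.7 expected events.

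*Combined protocol and SAP*

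**What the plan says.** Section 15.4 plans a center comparison on demographic variables and on endpoint data. The endpoint part reads "For the assessment of the primary endpoints, both of which are binary (Y/N or S/F) variables", followed by "a random-effects logistic regression will be used to assess the comparability of results across centers". No covariate is named. Small sites are merged: "Centers with fewer than 10 implants will be treated as a single center". The section attaches no threshold, consequence or sparse-data fallback to the result.

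Elsewhere the plan treats etiology as central to patency. Section 15.1 states "Enrollment will be stratified according to etiology of disease", with totals of 125 PT and 45 NT set for the pivotal arm as a whole; nothing balances them within center. Sections 15.7 and 15.8.1 give each stratum its own assumed rate, performance goal and fixed weight. Section 15.5.3 says the thrombotic/non-thrombotic mix in this disease is not known and puts its range at zero to about 50%.

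For safety, section 15.7.1 expects an event rate of about 1% in about 170 subjects. For gender, section 15.9.1 has one sentence: "A subgroup analysis will be performed to evaluate device performance across genders". Section 15.9 says that ancillary evaluations carry no hypothesis tests, only estimates with 95% confidence intervals.

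**The concern.** The primary efficacy test separates NT from PT, but the check on whether centers form one population is not said to. If centers recruit different shares of NT disease, their crude patency differs even when the stent performs identically everywhere. The reverse can also happen: a center with weak PT results and many NT patients can sit close to the overall rate and draw no attention.

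For safety, the question is whether a random-effects model by center can say anything with one or two events. At stake is how the center analyses are read, in particular whether a null result is taken as support for pooling.

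**Working it through.** **Inputs.** Assumed patency is 0.955 (NT) and 0.779 (PT), with goals 0.855 and 0.679 and weights 0.26 and 0.74 (sections 15.7 and 15.8.1). Quotas are 45 NT and 125 PT (15.1). There are 156 evaluable subjects (15.7), and "170 pivotal patients will be enrolled at approximately 45 centers worldwide" (section 8). The safety event rate is about 1%, with goal 0.94 and one-sided alpha 0.025 (15.7.1).

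**The plan's own figures first.**
- *Safety power.* With an exact binomial at n = 170, success requires at most 4 events. Exact alpha is 0.0226 and power at a 1% event rate is 0.971, so the stated power above 90% reproduces.
- *Efficacy power.* The weighted Z-test with 41 NT and 115 PT gives 0.850 by normal approximation and 0.869 by exact enumeration. This is in line with the stated 84% and the target of at least 85%.
- *Pooled patency.* 0.26 × 0.955 + 0.74 × 0.779 = 0.825. Section 15.5.3 prints about 85%, which these rates and weights do not give (its table weights of 0.25/0.75 give 0.823). I use 82.5%.

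**Case mix and crude patency.** For a center with NT share s and no center effect, patency = 0.779 + 0.176 × s.

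| NT share | Expected crude patency |
|---|---|
| 0% | 77.9% |
| 10% | 79.7% |
| 26% | 82.5% |
| 50% | 86.7% |

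Each 10-point difference in NT share moves crude patency by 1.76 points. The 0–50% range spans 8.8 points, against the 10-point delta that sets the performance goals. The range comes from section 15.5.3 and describes the disease, so applying it to centers is an assumption.

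**Masking.** Take a center with 50% NT whose true PT patency is 67.9%, the PT goal itself. Crude patency is 0.5 × 0.955 + 0.5 × 0.679 = 81.7%, against 82.5% overall.

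**Effect on the formal test.** Random-intercept logistic models were fitted to simulated data with no center effect: six centers of 15 plus one merged group of 66 (6 × 15 + 66 = 156). A likelihood-ratio statistic above 2.706 was counted as rejection (nominal 5%). This layout and the center mixes are assumed. Without a stratum term, rejection was about 1 to 2% with equal mix, and 4 to 5% with center NT shares spread over 0–60% or 0–80%. With a stratum term it was about 2 to 2.5% throughout. At 400 runs per scenario the Monte Carlo standard error is about 1 point, √(0.05 × 0.95/400) = 0.011. The test has little power, because only 41 × 0.045 + 115 × 0.221 = 27.3 patency failures are expected.

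**Sparse NT failures.** Expected NT failures are 41 × 0.045 = 1.8, or 45 × 0.045 = 2.0. The chance of none is 0.955^41 = 15%, or 0.955^45 = 13%. In that case an ordinary maximum-likelihood NT/PT coefficient is not finite.

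**Safety.** Expected events are 170 × 0.01 = 1.7. P(0) = 0.99^170 = 18%, P(≤1) = 49% and P(≤4) = 97%. In simulation (assumed six centers of 15 plus a merged group of 80), the estimated center variance was zero in about 71% of trials and the test rejected in 1.3%. When one 15-implant center truly had a 10% event rate, it was detected in only about 20%.

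**Gender.** Assume equal numbers of men and women and 26% NT overall. NT shares of 36% and 16% give a gap of 0.20 × 17.6 = 3.5 points with no gender effect; 46% and 6% give 7.0 points.

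**The case against.** The strongest reply is that nothing decisive rests on these analyses. Section 15.4 attaches no rule to the poolability result. The primary efficacy test already uses separate goals, fixed weights and stratum-specific variances, and section 15.7 adds observed-rate criteria within each stratum. All of this stands.

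The documents give no NT share by center or gender, so the size of any imbalance is assumed. Naming no covariate is also not the same as excluding one. The merging rule limits the problem further: with 170/45 = 3.8 patients per center on average, and at most 170/10 = 17 centers able to reach 10 implants, many sites would fall into one group whose mix tends toward the trial-wide 26%. These points stand too, and they are why the effect is called modest.

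A reader might infer that the patency check would often raise false alarms. The simulations with the planned type of model do not support that: even very unequal mixes brought rejection only to 4 to 5%. A reader might also infer that the safety model cannot be fitted. Strictly, no finite estimate exists only when there are no events (18%); otherwise software usually returns a fit, mostly with zero center variance.

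For gender, the text names no endpoint or model and allows no hypothesis test. It is missing reporting detail, and no formal false positive can arise.

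Finally, an NT/PT term meets its own sparse-data problem, and an exact by-center safety test on 1.7 expected events would have almost no power. Both limits are reflected in the fix.

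**Conclusion.** The concern holds in limited form. As written, the patency poolability model does not separate case mix from center effect, although the plan's own rates differ by 17.6 points between strata. The resulting spread in crude center patency, up to 8.8 points, rests on the assumed 95.5% and 77.9% and on centers spanning 0–50% NT. The practical loss lies mainly in interpretation, including the masking of a center with poor PT patency; false-signal inflation is small. Adding the term would not give the center test much power either.

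The safety model is uninformative at the planned event rate, and its non-significance should not be read as evidence that centers can be pooled. The primary efficacy conclusion is not affected. This is a worthwhile free improvement and does not challenge the design.

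**What to change.** 1. **Patency, section 15.4.** Add etiology (NT/PT) as a fixed effect in the random-effects logistic model, and show patency by stratum alongside the center results. State in advance what is done if there are no NT failures: either a penalized (Firth-type) fit, or a fixed offset from the assumed stratum rates, ln[(0.955/0.045)/(0.779/0.221)] = 1.795. The offset takes the planned difference as true and should be labeled so.
2. **Safety, section 15.4.** Replace the model with a by-center listing of events and implants, and state that absence of a significant center difference is not evidence of poolability.
3. **Gender, section 15.9.1 (optional).** Name the endpoint and show results by NT/PT or standardized to the 0.26/0.74 weights. Give counts: with an assumed 20 or so NT patients per gender, only 20 × 0.045 = 0.9 NT failures are expected in each.

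The cost is SAP wording and one model term. Etiology is already needed for every patient in the primary analysis, so no new data are required and the sample size does not change.
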